	
c) At any time through 12 months after the procedure:
 
• Re-ablation for AF, AFL* or AT;• Use of amiodarone, except intra-procedurally to control an arrhythmia. 
2. Proportion of PVs that achieve electrical isolation by using the FARAPULSE Pulsed Field Ablation System only.
 
3. Chronic success allowing AADs.
 
*excluding cavotricuspid isthmus (CTI)-dependent flutter confirmed by electrophysiology study
 
Secondary Safety Endpoint:
 
Proportion of subjects that free from primary safety events defined as above through 7 days after the procedure and free from the following serious procedure-related and/or device-related adverse events at any time through the completion of 12-month follow-up visit.
 
• Atrial esophageal fistula• Severe PV stenosis• Persistent phrenic nerve palsy* 
*The study will collect information on phrenic nerve palsy observed before the end of the index procedure and, in case of occurrence, will track information for potential recovery during data collection at the study visits.

Method of Assigning Patients to Treatment	This is a real-world study, subjects who sign the consent form and meet all key eligibility criteria will be enrolled.

A Real-world Study of the FARAPULSE Pulsed Field Ablation System in A Chinese Population with Paroxysmal Atrial Fibrillation (REPLACE Study)

Follow-up Schedule	
This is a retrospective and/or prospective observational study. For retrospectively enrolled subjects, data will be collected from each patient's scheduled and unscheduled follow-up visits for 12 months post-procedure per the standard of care follow-up schedule as defined by their center that performs the clinical follow-up visits.
 
For prospectively enrolled subjects, data collection at the following visits are recommended:
 
• Baseline Visit• Procedure• 7 days after the procedure (7-10 days) Telephone contact• 1 month after the procedure (30 ± 7 days) Telephone contact• 3 months after the procedure (91-104 days) Clinic visit• 6 months after the procedure (180 ± 30 days) Clinic visit• 12 months after the procedure (365 ± 30 days) Clinic visit
Study Duration	This is a retrospective and/or prospective study. The 12-month follow-up data will be collected after the procedure. The study duration is estimated up to 18 months depending on the precent of subjects enrolled prospectively.

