⁵ Phrenic Nerve Palsy Assessment at discharge and at follow-up visits is only applicable for subjects who had phrenic nerve palsy detected during the index or repeat procedure. Subjects should be assessed per standard of care; suggested means of assessment include a sniff test or an inhalation-exhalation chest radiography of the diaphragm.

⁶ If there is a clinical suspicion of stroke/TIA by the physician, then the data of neuro assessment, including but not limited to specialist consultation and brain MRI, will be collected.

⁷ Collect results if applicable, the absent of this assessment is not Protocol Deviation.

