10.9. Six Month Follow-up Visit (180 ± 30 days)

Discharged subjects will be assessed in person 6 month (180 ± 30 days) post-Index Procedure. For eligible subjects enrolled retrospectively, the Six-Month Follow-up Visit data collection may occur at the same day as Three-Month Follow-up Visit data collection. For eligible subjects enrolled prospectively, the Six Month Follow-up Visit should occur within 180 ± 30 days post Index Procedure. The data collection at the Six-Month Follow-up Visit includes:

- Date and time of visit, way to collect the data
- Cardiac physical assessment performed as standard of care including, heart rhythm, heart rate, systolic and diastolic blood pressure.
- 12-lead ECG
- 24-hour Holter Monitor
- Recurrent arrhythmia, cardioversions, ablations or hospital admissions including occurrence, date, indication and outcome of any intervention
- Any Stroke Evaluation for Neurologic Assessment, if applicable
- Subjects with unresolved phrenic nerve palsy detected at the discharge visit must be re-assessed per center's standard of care to evaluate if the event resolved
- Perform Cardiac CT/MRI if PV stenosis is suspected at any time throughout the follow-up period
- Medication information, including new, discontinued or changes in study-collected medication information (e.g., AADs and NOAC)
- Reportable Adverse Events, including resolution of ongoing events, if applicable
- Protocol Deviations, if applicable

10.10. *Twelve Month Follow-up Visit (365 ± 30 days)*

Discharged subjects will be assessed in person 12 month (365 ± 30 days) post-Index Procedure. For eligible subjects enrolled retrospectively, the Twelve-Month Follow-up Visit data collection may occur in the same day as Six-Month Follow-up Visit data collection. For eligible subjects enrolled prospectively, the Twelve Month Follow-up Visit should occur within 365 ± 30 days post Index Procedure. The data collection at the Twelve-Month Follow-up Visit includes:

- Date and time of visit, way to collect the data
- Cardiac physical assessment performed as standard of care including, heart rhythm, heart rate, systolic and diastolic blood pressure.
- 12-lead ECG and/or Holter
- Apply the 24-hour Holter monitor on the subject and instruct subject to submit their heart rhythm
- Recurrent arrhythmia, cardioversions, ablations or hospital admissions including occurrence, date, indication and outcome of any intervention
- Any Stroke Evaluation for Neurologic Assessment, if applicable

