10.16. Local vendor documentation

This study requires a vendor. Appropriate certifications and documentation records are required to be maintained at the site for vendor.

11. Statistical Considerations

11.1. *Endpoints*

11.1.1. *Primary Endpoints*

11.1.1.1. *Primary Safety Endpoint*

The primary safety endpoint at 30 days consists of acute primary safety endpoint events as defined in **Section 6**, which will be assessed after all the enrolled subjects finishing One-month Visit data collection.

11.1.1.1.1 *Hypothesis*

This is an observational real-world study with small sample size, no formal hypothesis is performed in this study.

11.1.1.1.2 *Sample Size*

There is no formal hypothesis for this study, thus no sample size calculation is performed in this study. The study device has achieved CE mark and accumulated a large amount of clinical data. This trial with 30 PAF subjects will be used to produce data in Chinese population.

The following table provides a 95% confidence interval (exact methods) for a sample size of 30 if there are 0 ~ 3 primary safety events.

Safety Events	Rates (n=30)	Lower 95%CI	Upper 95%CI
0	0%	0%	11.6%
1	3.3%	0.1%	17.2%
2	6.7%	0.8%	22.1%
3	10%	2.1%	26.5%

11.1.1.1.3 *Statistical Methods*

Descriptive statistics will be conducted for the safety endpoint events. The number, incidence (amount of events/number of subjects) and its 95% confidence interval (exact methods) will be calculated. The primary safety endpoints will be analyzed for ATTEMPT and TREATMENT subjects in the ITT set. Explorative statistical analysis might be produced if appropriate, e.g., Bayesian estimation of the study results using FARAPULSE IDE data as the prior.

11.1.1.2. *Primary Effectiveness Endpoint*

The primary effectiveness endpoint is the acute procedural success, defined as proportion of subjects that achieved PVI with FARAPULSE Pulsed Filed Ablation system only, which will be assessed after all the enrolled subjects finishing One-month Visit data collection.

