11.1.2. Secondary Endpoints

11.1.2.1. Secondary Safety Endpoints

The secondary safety endpoint will evaluate the proportion of subjects that free from primary safety events defined in **Section 6** through 7 days after the procedure and free from the following serious procedure-related and/or device-related adverse events at any time through the completion of 12-month follow-up visit, which will be assessed at the time of the twelve-month analysis:

- Atrial esophageal fistula
- Severe PV stenosis
- Persistent phrenic nerve palsy*

**The study will collect information on phrenic nerve palsy observed before the end of the index procedure and, in case of occurrence, will track information for potential recovery during the study visits.*

11.1.2.2. Secondary Effectiveness Endpoint 1

The first secondary effectiveness endpoint will evaluate the chronic success, which is defined as proportion of subjects that free from effectiveness events defined as failure as below at twelve months post-procedure.

Effectiveness events determining a failure are defined as:

- Fail to achieve electrical isolation of all PVs using FARAPULSE Pulsed Filed Ablation system only.
- After the Blanking Period to 12-month after the procedure:

- a) Occurrence of any Detectable AF, AFL* or AT captured by one of the following methods: ≥ 30 seconds in duration recording from 24-hour or longer Holter Monitor or ≥ 10 seconds recording from 12-lead ECG.
- b) Any cardioversion for AF, AFL* or AT.
- c) Use of any Class I or Class III AADs[#] for the treatment of AF, AFL* or AT.
- At any time through 12 months after the procedure:
 - a) Re-ablation for AF, AFL* or AT.
 - b) Use of amiodarone, except intra-procedurally to control an arrhythmia.

#It won't be considered as a failure if the subject has three-month visit happened after 90 days post the procedure, but still in the window (≤ 104 day) with AADs on, and physicians decide to take AADs off after this visit.

**excluding CTI-dependent flutter confirmed by EP study*

11.1.2.3. Secondary Effectiveness Endpoint 2

The second secondary effectiveness endpoint will evaluate the proportion of PVs that achieve electrical isolation by using the FARAPULSE Pulsed Field Ablation system only.

11.1.2.4. Secondary Effectiveness Endpoint 3

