11.2.4. Number of Subjects per Investigative Site

Thirty ATTEMPT or TREATMENT subjects will be enrolled from one site.

11.3. Data Analyses.

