3.2.3 Statistical Methods

Descriptive statistics will be conducted for the safety endpoint events. The number, incidence (amount of events/number of subjects) and its 95% confidence interval (exact methods) will be calculated. The primary safety endpoints will be analyzed for ATTEMPT and TREATMENT subjects in the ITT set. Explorative statistical analysis might be produced if appropriate, e.g., Bayesian estimation of the study results using FARAPULSE IDE data as the prior.

3.3 Secondary Effectiveness Endpoint:

1. Chronic Success: Proportion of subjects that free from effectiveness events defined as failure as below at 12 months post-procedure.

Effectiveness events determining a failure are defined as:

- Fail to achieve electrical isolation of all PVs using FARAPULSE Pulsed Field Ablation system only.
- After the Blanking Period (90 days post the procedure) to 12-month after the procedure
 - a) Occurrence of any Detectable AF, AFL* or AT captured by one of the following methods: ≥ 30 seconds in duration recording from 24-hour Holter Monitor or ≥ 10 seconds recording from 12-lead ECG, or
 - b) Any cardioversion for AF, AFL* or AT, or
 - c) Use of any Class I or Class III AADs[#] for the treatment of AF, AFL* or AT.

- At any time through 12 months after the procedure:
 - a) Re-ablation for AF, AFL* or AT, or
 - b) Use of amiodarone, except intra-procedurally to control an arrhythmia.
- 2. Proportion of PVs that achieve electrical isolation by using the FARAPULSE Pulsed Field Ablation system only.
- 3. Chronic success allowing AADs.

#It won't be considered as a failure if the subject has three-month visit happened after 90 days post the procedure, but still in the window (<=104 day) with AADs on, and physicians decide to take AADs off after this visit.

**excluding CTI-dependent flutter confirmed by EP study.*

3.4 Secondary Safety Endpoint:

Proportion of subjects that free from primary safety events defined as above through 7 days after the procedure and free from the following serious procedure-related and/or device-related adverse events at any time through the completion of 12-month follow-up visit.

- Atrial oesophageal fistula
- Severe PV stenosis
- Persistent phrenic nerve palsy*

**The study will collect information on phrenic nerve palsy observed before the end of the index procedure and, in case of occurrence, will track information for potential recovery during the study visits.*

3.5 Additional Endpoints:

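### Chronic success does not depend on any rhythm recording after day 90, and its 12-month cut-off has no day number although the visit window runs to day 395

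*Protocol*

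**What the plan says.** Protocol 6.2.2.1 and 11.1.2.2 and SAP 3.3 define chronic success as freedom from listed failure events. The arrhythmia event is "Occurrence of any Detectable AF, AFL* or AT captured by one of the following methods": at least 30 seconds on Holter or at least 10 seconds on a 12-lead ECG. SAP 3.3 sets its period as "After the Blanking Period (90 days post the procedure) to 12-month after the procedure". Protocol 11.1.2.4 uses the same arrhythmia event and period for chronic success allowing AADs, and drops the AAD and amiodarone failures.

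On recordings:
- Table 10.1-1 marks a 12-lead ECG at 3, 6 and 12 months and a Holter at 6 and 12 months. The 3-month Holter, and the baseline and unscheduled ECG and Holter, carry footnote 7: "Collect results if applicable, the absent of this assessment is not Protocol Deviation".
- The synopsis says that data for retrospective subjects come from visits "per the standard of care follow-up schedule as defined by their center that performs the clinical follow-up visits". For prospective subjects the listed visits are recommended.
- Section 10.10 lists "12-lead ECG and/or Holter" and then, in a separate bullet, the application of a 24-hour Holter. It also says that the "Twelve Month Follow-up Visit should occur within 365 ± 30 days post Index Procedure".

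On analysis, Protocol 11.3.2 gives a simple proportion with an exact 95% interval. Protocol 11.2.3 and SAP 7.4 fill missing values for primary endpoints only. SAP 7.3 adds that patients completing the visit are considered in denominators, within a rule about baseline variables.

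The secondary safety endpoint (Protocol 11.1.2.1, SAP 3.4) runs until the 12-month visit has been completed.

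**The concern.** An endpoint defined by absence of captured events treats 'looked and found nothing' and 'did not look' alike. A subject who attends at 12 months, has had no ECG or Holter since day 90, and has no AAD use, cardioversion or re-ablation meets every condition for success. The error goes one way: missing recordings can only raise the rate.

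These two endpoints are the study's only 12-month rhythm results, and the study is meant to support registration in China (Protocol 4.2 and 7.3). Chronic success allowing AADs is the more exposed, because an unrecorded recurrence treated with drugs no longer surfaces as a failure. If recording differs by enrolment route, the planned prospective/retrospective subgroup would mix detection with device effect.

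The second problem is the cut-off. The last scheduled Holter may be applied up to day 395, but the effectiveness period ends at an unnumbered 12 months. AF found on day 380 could be counted or not, and that choice could be made after the result is known.

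**Working it through.** **1. The plan's own figure.** The only interval calculation in the documents is for primary safety: "The following table provides a 95% confidence interval (exact methods) for a sample size of 30 if there are 0 ~ 3 primary safety events". Clopper-Pearson limits reproduce it: 0/30 gives 0-11.6%, 1/30 gives 0.1-17.2%, 2/30 gives 0.8-22.1% and 3/30 gives 2.1-26.5%. No corresponding figure is given for chronic success.

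**2. Following one subject through the rules.** Take a TREATMENT subject with all PVs isolated, a completed 12-month visit, no ECG or Holter after day 90 and no other failure event.
- Failure definition (Protocol 11.1.2.2): no event captured, so no failure.
- Missing-data rule (Protocol 11.2.3, SAP 7.4): not a primary endpoint, so nothing is filled.
- Denominator rule (SAP 7.3), if it applies here: the visit was completed, so the subject stays in.
- Analysis (Protocol 11.3.2): simple proportion, so no censoring.

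The subject is counted as a success. The enrolment route makes no difference.

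**3. Possible size.** Let s be the true success rate and m the share of subjects with no recording, all of whose recurrences go undetected. Then

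apparent rate = 1 - (1 - s)(1 - m), and inflation = m(1 - s).

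For s, Protocol 4.1.3 gives one-year freedom from AF/AFL/AT of 78.5% (whole pooled cohort) and 84.5% (optimized waveform). The documents do not give m; 10-30% is assumed.

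| m | s = 78.5% | inflation | s = 84.5% | inflation |
|---|---|---|---|---|
| 10% | 80.65% | 2.15 points | 86.05% | 1.55 points |
| 20% | 82.80% | 4.30 points | 87.60% | 3.10 points |
| 30% | 84.95% | 6.45 points | 89.15% | 4.65 points |

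Example: 1 - 0.215 x 0.70 = 0.8495.

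**4. What the scoring choice does to a reported result.** Section 11.2.4 says: "Thirty ATTEMPT or TREATMENT subjects will be enrolled from one site". Assume that all 30 are TREATMENT subjects, that 24 have no recorded failure, and that k of those 24 have no recording after day 90. Exact 95% intervals are in brackets.

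| k | counted as success | excluded | counted as failure |
|---|---|---|---|
| 3 | 24/30 = 80.0% (61.4-92.3) | 21/27 = 77.8% (57.7-91.4) | 21/30 = 70.0% (50.6-85.3) |
| 6 | 24/30 = 80.0% (61.4-92.3) | 18/24 = 75.0% (53.3-90.2) | 18/30 = 60.0% (40.6-77.3) |
| 9 | 24/30 = 80.0% (61.4-92.3) | 15/21 = 71.4% (47.8-88.7) | 15/30 = 50.0% (31.3-68.7) |

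Under the plan's scoring the result is the same whatever k is, so a reader cannot see the gap.

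**5. The cut-off.** The window is 365 - 30 = 335 to 365 + 30 = 395, which is 395 - 335 + 1 = 61 days. If 12 months means day 365, days 366-395 lie beyond it: 30 days, and 30/61 = 49%. This counts calendar days and is not a forecast of when visits will fall.

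**The case against.** The strongest reply is that the recordings are scheduled. Table 10.1-1 makes no exception for retrospective subjects, and sections 10.8 to 10.10 name those subjects and then give one data list for all. Protocol 17.2 says that the ECG and Holter match routine practice. Where retrospective data may be unavailable, the protocol says so (10.5.2 and 12.3), and it does not say so here. This stands. A reader might infer that no recording after day 90 is called for in retrospective subjects, or that footnote 7 waives the later ones. The documents support neither: footnote 7 is not attached to the 3-, 6- or 12-month ECG or to the 6- or 12-month Holter. Nor does section 10.10 make the 12-month Holter optional, since it has its own bullet; the mismatch with the table concerns the ECG. But a scheduled recording that was not made still leaves the subject a success.

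On the cut-off, a reader might infer that a Holter on days 366-395 falls outside the endpoint. That is not established. Twelve months is never defined as day 365, the synopsis labels the visit as 12 months (365 ± 30 days), and section 10.13 follows subjects until that visit is completed. The period is ambiguous; those days are not clearly excluded.

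The plan also looks at missingness separately for prospectively and retrospectively collected data (Protocol 11.2.3, SAP 7.4). That helps, but it does not change how the endpoint is scored. Finally, this is a descriptive secondary endpoint in a small study without hypotheses, which limits the consequence but does not remove the bias.

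**Conclusion.** The concern holds as a scoring gap. Neither 12-month effectiveness endpoint depends on a recording after day 90, and no missing-data rule covers them. Under the written definition, subjects with no recording and no other failure event count as successes, whichever way they were enrolled. The direction of bias is upward.

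The size is unknown. The illustration of about 80.7-85.0% for a true 78.5% rests on an assumed 10-30% unrecorded share and on none of those recurrences surfacing through another failure event. The 78.5% is also freedom from arrhythmia, not this composite. A reader might take the range as an estimate of bias in this study; the documents give no basis for that. With 30 subjects, each reclassified subject moves the rate by 1/30 = 3.3 points.

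The end of the effectiveness period is undefined for 30 of the 61 permitted visit days, whereas the secondary safety endpoint is tied to visit completion.

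**What to change.** In Protocol 6.2.2.1, 11.1.2.2 and 11.1.2.4 and SAP 3.3:

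1. State that the effectiveness period runs from day 91 through the later of day 365 and completion of the in-window 12-month visit, including the Holter applied at that visit. Ending at visit completion alone would drop events up to day 365 for subjects seen on days 335-364.
2. Score a subject without a failure event as a success only if at least one qualifying Holter or 12-lead ECG was obtained after day 90. Report the others as 'rhythm not assessed', and give a sensitivity analysis counting them as failures. Use one definition of a qualifying Holter: 11.1.2.2 and 11.1.2.4 admit recordings longer than 24 hours, while 6.2.2.1 and SAP 3.3 mention only 24-hour Holter.
3. Tabulate the number and timing of recordings after day 90 by enrolment route. One early ECG would satisfy item 2, so this table shows how thorough the monitoring was. Reconcile "12-lead ECG and/or Holter" in section 10.10 with Table 10.1-1, which marks both.

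The cost is an amendment to both documents before the 12-month analysis, which SAP 5.5 provides for on the SAP side, and one extra table. No test is added. The reported rate may be lower, the assessed denominator smaller, and the period up to 30 days longer for subjects seen late in the window.

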11.1.3. Additional Endpoints

1. AF symptoms assessment: Descriptive analysis of atrial fibrillation symptoms at baseline versus 12 months after the procedure.
2. Procedural parameters:

- Total procedure time (initiation of interventional venous access puncture to all devices removed from the body)
- Left atrial dwell time (total time an ablation catheter is in the left atrium)
- Total ablation time (first ablation to last ablation for PVI)
- Fluoroscopy time (total duration of exposure)

11.2. General Statistical Methods

Descriptive statistics will be conducted for the primary, secondary and other endpoint events. When descriptive statistics are used, continuous variables will be summarized using standard quantitative statistics: number of available observations, mean, standard deviation, median, quartiles and range (minimum and maximum observed values) and its 95% confidence interval. Categorical variables will be summarized using the number, incidence (amount of events/number of subjects) and its 95% confidence interval (exact methods).

Explorative statistical analysis might be produced if appropriate, e.g., Bayesian estimation of the study results using FARAPULSE IDE data as the prior.

11.2.1. Analysis Sets

ITT set will involve subjects who have signed informed consent and satisfied with all key criteria. Primary effectiveness endpoints will be summarized for TREATMENT subjects in mITT set.

Secondary effectiveness endpoints will be summarized for TREATMENT subjects in ITT set and mITT set respectively.

Primary and secondary safety endpoints will be summarized for ATTEMPT and TREATMENT subjects in ITT set.

The additional endpoints will be summarized for TREATMENT subjects in ITT set.

11.2.2. Control of Systematic Error/Bias

This is a real-world study. Selection of patients will be made from the Investigational site's routine patients. All patients meeting the key eligibility criteria and having signed the ICF will be eligible for enrollment in the study. Control and reduction of potential bias associated with a single-arm study design have been taken into account by defining key inclusion and exclusion criteria to represent a population similar to the patients with AF ablation in the real world and defining a mITT group with population similar to the subjects enrolled in ongoing ADVENT trial and other trials about AF ablation.

